5.3. Lifestyle Considerations

Potential participants must be willing and able to adhere to the following lifestyle restrictions during the course of the study to be eligible for participation:

- 1. Refer to Section 6.8, Concomitant Therapy for details regarding prohibited and restricted therapy during the study.
- 2. Agree to follow all requirements that must be met during the study as noted in the Inclusion and Exclusion Criteria (eg, contraceptive requirements).

5.4. Screen Failures

Participant Identification, Enrollment, and Screening Logs

The investigator agrees to complete a participant identification and enrollment log to permit easy identification of each participant during and after the study. This document will be reviewed by the sponsor study site contact for completeness.

The participant identification and enrollment log will be treated as confidential and will be filed by the investigator in the study file. To ensure participant confidentiality, no copy will be made. All reports and communications relating to the study will identify participants by participant identification and age at initial informed consent. In cases where the participant is not randomized into the study, the date seen and age at initial informed consent will be used.

Individuals who do not meet the criteria for participation in this study (screen failure) may be rescreened.

Rescreening

Individuals who do not meet the criteria for participation in this study (screen failure) may be rescreened 1 time.

5.5. Criteria for Temporary Delaying Enrollment/Randomization/Administration of Study Intervention Administration

This section is not applicable for this study.

6. STUDY INTERVENTION AND CONCOMITANT THERAPY

6.1. Study Intervention(s) Administered

Participants will be randomly assigned in a 1:1 ratio to 1 of the following study intervention groups:

- Guselkumab (Group/Arm A): Guselkumab 400 mg IV administration Weeks 0, 4, and 8 (induction) followed by guselkumab 200 mg SC administration Q4W from Week 12 until Week 48 (maintenance).
- Placebo (Group/Arm B): Matching placebo IV administration Weeks 0, 4, and 8 (induction) followed by matching placebo SC administration Q4W from Week 12 until Week 48 (maintenance).

Intravenous study intervention (including the flush) should be administered over a period of not less than 1 hour, and not more than 2 hours. The infusion (including the flush) should be completed within 6 hours of preparation.

Since 2 SC injections by using 100 mg/mL prefilled syringe (PFS) are administered at visits, each injection of study intervention should be given at a different location of the body.

Study intervention administration must be captured in the source documents and the electronic case report form (eCRF).

Guselkumab will be manufactured and provided under the responsibility of the sponsor. Refer to the IB for a list of excipients.

During the LTE, participants will receive guselkumab treatment in LTE as below depending on the arms they were in the main study:

- Group/Arm A (guselkumab arm from the main study): Guselkumab 200 mg SC and placebo IV at LTE Weeks 52, 56, and 60 followed by guselkumab 200 mg SC Q4W from LTE Week 64 until Week 100.
- Group/Arm B (placebo arm from the main study): Placebo SC and guselkumab 400 mg IV at LTE Weeks 52, 56, and 60 followed by guselkumab 200 mg SC Q4W from LTE Week 64 until Week 100.

After Week 68 participants who have been appropriately trained in the self-administration of study intervention may self-administer study intervention. At-home administration is allowed for selected visits. More details are provided in Section 4.1.2 Self-Administration of Study Intervention.

6.1.1. Combination Products

For this protocol, the term combination product refers to the single integral drug-device combination.

The sponsor-manufactured combination product for use in this study is the prefilled syringe (PFS) assembled with an UltraSafe PlusTM Passive Needle Guard (PFS-U). Additional details on the PFS-U are provided in Section 6.2.

All combination product deficiencies (including failure, malfunction, improper or inadequate design, manufacturer error, use error, and inadequate labeling) shall be documented and reported

by the investigator throughout the study. These deficiencies will be reported as product quality complaints (PQC) (see Section 10.4.6, Product Quality Complaint Handling) and appropriately managed by the sponsor.

6.2. Preparation/Handling/Storage/Accountability

Preparation/Handling/Storage

For IV administrations, guselkumab final vialed product (FVP [IV]) is supplied as a sterile solution in a single-use glass vial containing 20 mL at a concentration of 10 mg/mL. Study intervention will be prepared for IV administration based on the instructions provided to clinical sites in the IPPI.

For SC administrations, guselkumab will be supplied as a 100 mg/mL sterile solution in a single-use PFS assembled in an UltraSafe PlusTM Passive Needle Guard (PFS-U). For SC administration, placebo for guselkumab will be supplied as a 1 mL sterile solution in a single-use PFS assembled in a PFS-U.

Guselkumab and placebo for guselkumab should be clear and colorless to light yellow solution that may contain small translucent particles. Do not use guselkumab or placebo for guselkumab if the liquid is cloudy or discolored or has large particles. Protection from light is not required during the preparation and administration of the study intervention material, but avoid direct exposure to sunlight. Aseptic technique must be used during the preparation and administration of the study intervention material.

Study personnel will instruct participants on how to transport, store, and administer study intervention for at-home use during the LTE as indicated for this protocol.

Refer to the Investigational Product Procedures Manual (IPPM) and Investigational Product Procedure Instructions (IPPI) for additional guidance on study intervention preparation, handling, and storage.

Accountability

The investigator is responsible for ensuring that all study intervention received at the site is inventoried and accounted for throughout the study. The study intervention administered to the participant must be documented on the intervention accountability form. All study intervention will be stored and disposed of according to the sponsor's instructions. Study site personnel must not combine contents of the study intervention containers.

Study intervention must be handled in strict accordance with the protocol and the container label, and must be stored at the study site in a limited-access area or in a locked cabinet under appropriate environmental conditions. Unused study intervention must be available for verification by the sponsor's study site monitor during on-site monitoring visits. The return to the sponsor of unused study intervention will be documented on the intervention return form. When the study site is an authorized destruction unit and study intervention supplies are destroyed on-site, this must also be documented on the intervention return form.

Potentially hazardous materials containing hazardous liquids, such as needles and syringes should be disposed of immediately in a safe manner and therefore will not be retained for intervention accountability purposes.

Study intervention should be dispensed under the supervision of the investigator or a qualified member of the study site personnel, or by a hospital/clinic pharmacist. Study intervention will be supplied only to participants participating in the study. Returned study intervention must not be dispensed again, even to the same participant. Study intervention may not be relabeled or reassigned for use by other participants. The investigator agrees neither to dispense the study intervention from, nor store it at, any site other than the study sites agreed upon with the sponsor. Further guidance and information for the final disposition of unused study interventions are provided in the IPPI.

Participants who will be self-administering study intervention at home will receive detailed instructions for study intervention storage and disposal of used syringes and handling of unused study material. These participants will receive a sharps container to dispose of used syringed and will be instructed to return the sharps container and/or unused cartons with syringes. Participants who self-administer at home will record study intervention administrations with time and date information on a diary card.

6.3. Measures to Minimize Bias: Randomization and Blinding

Intervention Allocation

Procedures for Randomization and Stratification

Central randomization will be implemented in this study. Participants will be randomly assigned to 1 of 2 intervention groups based on a computer-generated randomization schedule prepared before the study by or under the supervision of the sponsor. The randomization will be balanced by using randomly permuted blocks and will be stratified by presence of ILD (yes, no), baseline mRSS (low [\geq 10 to \leq 15] or high [\geq 16 to \leq 22]), and baseline anti-topoisomerase I antibody status (positive, negative). The interactive web response system (IWRS) will assign a unique intervention code, which will dictate the intervention assignment and matching study intervention kit for the participant. The requestor must use his or her own user identification and personal identification number when contacting the IWRS, and will then give the relevant participant details to uniquely identify the participant.

Blinding

To maintain the study blind, the study intervention container will have a label containing the study name, study intervention number, and reference number. A tear-off label is designed to be torn off, separated from the study intervention container, and attached to the participant's source documents. The label will not identify the study intervention in the container. However, if it is necessary for a participant's safety, the study blind may be broken and the identity of the study intervention ascertained. The study intervention number will be entered in the eCRF when the study

intervention is administered. The study interventions will be identical in appearance and will be packaged in identical containers.]

The investigator will not be provided with randomization codes. The codes will be maintained within the IWRS, which has the functionality to allow the investigator to break the blind for an individual participant.

Data that may potentially unblind the intervention assignment (ie, study intervention serum concentrations, anti-guselkumab antibodies, study intervention preparation/accountability data, intervention allocation, and biomarker or other specific laboratory data) will be handled with special care to ensure that the integrity of the blind is maintained and the potential for bias is minimized. This can include making special provisions, such as segregating the data in question from view by the investigators, clinical team, or others as appropriate until the time of database lock (DBL) and unblinding.

All sponsor personnel, site personnel and participants will remain blinded to the treatment assignments until the Week 52 DBL.

The investigator may in an emergency determine the identity of the intervention by contacting the IWRS. While the responsibility to break the intervention code in emergency situations resides solely with the investigator, it is recommended that the investigator contact the sponsor or its designee if possible, to discuss the particular situation, before breaking the blind. Telephone contact with the sponsor or its designee will be available 24 hours per day, 7 days per week. In the event the blind is broken, the sponsor must be informed as soon as possible. The date, time, and reason for the unblinding must be documented by the IWRS, in the appropriate section of the eCRF and in the source document. The documentation received from the IWRS indicating the code break must be retained with the participant's source documents in a secure manner.

Participants who have had their intervention assignment unblinded should continue to return for scheduled evaluations.

6.4. Study Intervention Compliance

Study intervention will be administered at site as an IV infusion or SC injection by qualified staff. The details of each administration will be recorded in the eCRF. For IV infusions, this will include date and start and stop times of the IV infusion and volume infused; for SC injections, this will include date and time of SC injection.

Study site personnel will maintain a log of all study intervention administered. Study intervention supplies for each participant will be inventoried and accounted for.

6.5. Dose Modification

No treatment/dose adjustment of study intervention will be permitted throughout the study period.

6.6. Continued Access to Study Intervention After the End of the Study

This protocol is designed to provide participants with up to approximately 104 weeks of treatment, including LTE.

No continued access is proposed for this study as this is a PoC study. At the end of their participation in the study, the participants will be instructed that they should return to their primary physician to determine standard of care, if applicable.

6.7. Treatment of Overdose

For this study, any dose of guselkumab greater than the highest dose at a single visit specified in this protocol will be considered an overdose. The sponsor does not recommend specific treatment for an overdose.

In the event of an overdose, the investigator or treating physician should:

- Contact the Medical Monitor immediately.
- Evaluate the participant to determine, in consultation with the Medical Monitor, whether study intervention should be interrupted or whether the dose should be reduced.
- Closely monitor the participant for AE/SAE and laboratory abnormalities until guselkumab can no longer be detected systemically.
- Obtain a plasma sample for PK analysis if requested by the Medical Monitor (determined on a case-by-case basis).
- Document the quantity of the excess dose as well as the duration of the overdosing in the eCRF.

6.8. Concomitant Therapy

Prestudy therapies including specific SSc therapies administered up to 60 days before first dose of study intervention must be recorded at screening.

Concomitant therapies including specific SSc therapies must be recorded throughout the study beginning with start of the screening to the final safety follow-up visit. Concomitant therapies should also be recorded beyond the final safety follow-up visit only in conjunction with SAEs that meet the criteria outlined in Serious Adverse Events in Section 8.3.1, Time Period and Frequency for Collecting Adverse Event and Serious Adverse Event Information.

All therapies (prescription or over-the-counter medications, including vaccines, vitamins, herbal supplements; non-pharmacologic therapies such as electrical stimulation, acupuncture, special diets, exercise regimens, or other specific categories of interest) different from the study intervention must be recorded in the eCRF. Recorded information will include a description of the type of therapy, duration of use, dosing regimen, route of administration, and indication. Modification of an effective preexisting therapy should not be made for the explicit purpose of entering a participant into the study. Any questions or concerns with the use of concomitant therapies should be discussed with the study sponsor and/or medical monitor.

NSAIDs or Other Analgesics

Participants may be treated with NSAIDs, including COX-2 inhibitors, during the study. The participant's standing dose should remain stable during the study, unless dose reduction is required for safety reasons. The choice and doses of NSAIDs are at the discretion of the investigator. For participants who receive corticosteroids and/or NSAIDs, prophylactic treatment such as rebamipide, or H2-receptor blockers should be considered. Prophylactic treatment should be added according to the investigator's discretion.

Oral Corticosteroids

Participants may receive corticosteroids at a stable dose of ≤ 10 mg/day of prednisolone or equivalent during the study. Increases in corticosteroid doses for treatment of SSc are not allowed during the study. To treat non-SSc-related conditions such as asthma, increased doses of oral corticosteroids of up to 20 mg of prednisone daily (or equivalent) for 2 weeks are permitted. The dose of the corticosteroid should be tapered down to the previous level as rapidly as medically possible.

Medications for Pulmonary Arterial Hypertension

Participants may be treated with following medications for pulmonary arterial hypertension: endothelin receptor antagonists (eg, bosentan, ambrisentan and macitentan), phosphodiesterase 5 inhibitors (eg, sildenafil and tadalafil), and prostacyclins (eg, epoprostenol, iloprost and treprostinil). The dose should remain stable during the study.

ACE Inhibitors, Calcium-Channel Blockers, or Protein-Pump Inhibitors

Participants receiving ACE inhibitors, calcium-channel blockers, proton-pump inhibitors, and/or oral vasodilators have to be on a stable dose during the study, unless dose adjustments are required for safety reasons.

Prohibited and restricted therapies

During the study

IL-23 inhibitor therapy (including but not limited to guselkumab, risankizumab, tildrakizumab, brazikumab, mirikizumab)

tocilizumab

sirukumab, sarilumab, mavrilimumab, abatacept, belimumab

IL-12/23 inhibitors (ustekinumab)

IL-17 inhibitors (secukinumab, ixekizumab, brodalumab)

tyrosine kinase inhibitor (nintedanib)

Any live viral or live bacterial vaccination

Rituximab

Any cytotoxic agents (cyclophosphamide, chlorambucil, nitrogen mustard, or other alkylating agents)

Intravenous immunoglobulin (IVIG), apheresis therapy (plasmapheresis or leukopheresis)

Systemic immunosuppressive agents (including but not limited to cyclosporine A, azathioprine, tacrolimus, sirolimus, methotrexate, sulfasalazine, leflunomide with cholestyramine washout or mycophenolate mofetil/mycophenolic acid)

Intramuscular, intra-articular, intrabursal, epidural, intra-lesional or IV GCs

Pirfenidone

Systemic and topical Janus kinase inhibitors (eg, tofacitinib, upadacitinib)

Other biologics

Any investigational agents/treatments

The sponsor must be notified in advance (or as soon as possible thereafter) of any instances in which prohibited therapies are administered.

Rescue Medication

In the event that a participant experiences worsening criteria (Criteria: increase from baseline ≥5 in mRSS), investigators will have the option to treat with protocol-allowed rescue therapy after Week 24.

Oral Corticosteroid ≤20 mg/day of prednisolone or equivalent

Immunomodulator (Azathioprine), within the approved dose for SSc

If rescue therapy as stipulated above fails to control SSc symptoms sufficiently, the investigator should consider discontinuing the patient from the study.

7. DISCONTINUATION OF STUDY INTERVENTION AND PARTICIPANT DISCONTINUATION/WITHDRAWAL

7.1. Discontinuation of Study Intervention

A participant's study intervention must be discontinued if:

- The participant withdraws consent to receive study intervention.
- The investigator believes that for safety reasons or tolerability reasons (eg, AE) it is in the best interest of the participant to discontinue study intervention.
- The investigator or sponsor believes that there are no further benefit of continuing the study for the participants.
- The participant becomes pregnant or planning to become pregnant while enrolled in this study or within 12 weeks after the last administration of study intervention.
- Noncompliance with study intervention administration.
- The participant initiates treatment with prohibited therapies listed in Section 6.8 unless agreed upon with the sponsor medical monitor.

• The participant is deemed ineligible according to the following TB screening criteria:

A diagnosis of active TB is made.

A participant has symptoms suggestive of active TB based on follow-up assessment questions and/or physical examination or has had recent close contact with a person with active TB and cannot or will not continue to undergo additional evaluation.

A participant undergoing evaluation has a chest radiograph or chest CT with evidence of current active TB and/or a positive QuantiFERON-TB test or T-SPOT test result, unless active TB can be ruled out and appropriate treatment for latent TB can be initiated prior to the next study intervention administration and continued to completion (see also Section 8.2.9). Indeterminate QuantiFERON-TB test or borderline T-SPOT results should be handled as in Section 8.2.9. Participants with persistently indeterminate QuantiFERON-TB test results or borderline T-SPOT may continue without treatment for latent TB if active TB is ruled out, their chest radiograph or chest CT shows no abnormality suggestive of TB (active or old, inactive TB) and the participant has no additional risk factors for TB as determined by the investigator. This determination must be promptly reported to the sponsor and recorded in the participant's source documents and initialed by the investigator.

A participant receiving treatment for latent TB discontinues this treatment prematurely or is noncompliant with the therapy.

- The participant has a serious adverse reaction that is related to an injection or an infusion, including an injection-site or infusion reaction, resulting in bronchospasm with wheezing and/or dyspnea that requires ventilatory support OR that results in symptomatic hypotension with a decrease in systolic blood pressure >40 mm Hg.
- The participant has a reaction resulting in myalgia and/or arthralgia with fever and/or rash (suggestive of serum sickness and not representative of signs and symptoms of other recognized clinical syndromes) occurring 1 to 14 days after an injection of study intervention. These may be accompanied by other events including pruritus, facial, hand, or lip edema, dysphagia, urticaria, sore throat, and/or headache.
- The participant has severe liver test abnormalities that are not transient and are not explained by other etiologies. Such abnormalities would include (see Section 10.6, Appendix 6: Liver Safety: Suggested Actions and Follow-up Assessments):

Alanine aminotransferase (ALT) or aspartate aminotransferase (AST) $\geq 5 \times \text{ULN}$.

ALT or AST \geq 3 × ULN for more than 4 weeks.

ALT or AST $\ge 3 \times ULN$ and cannot be monitored weekly for 4 weeks.

ALT or AST \ge 3 × ULN and TBL \ge 2 × ULN or international normalized ratio [INR] >1.5 (INR not acceptable for participants on anticoagulants).

ALT or AST $\ge 3 \times$ ULN and symptoms (new or worsening) believed to be related to liver injury (such as fatigue, nausea, vomiting, right upper quadrant pain or tenderness, or jaundice) or hypersensitivity (such as fever, rash or eosinophilia).

• The participant has a malignancy including squamous cell skin cancer. Consideration may be given to allowing participants who develop ≤2 basal cell skin cancers that are adequately treated with no evidence of residual disease to continue to receive study intervention.

Discontinuation of a participant's study intervention must be strongly considered under the following conditions:

- The participant develops a serious infection, including but not limited to sepsis or pneumonia.
- The participant develops a severe injection-site or infusion reaction.

If a participant discontinues study intervention for any reason before the end of the double-blind phase, then the assessments should be obtained as specified in the SoA (Section 1.3). Study intervention assigned to the participant who discontinued study intervention may not be assigned to another participant. Additional participants will not be entered.

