6.11. Appendix 11 A Prohibited Change in SSC Medication

- New start of prohibited and restricted therapies during the study which are defined in the protocol Section 6.8:
 - IL-23 inhibitor therapy (including but not limited to guselkumab, risankizumab, tildrakizumab, brazikumab, mirikizumab)
 - tocilizumab
 - sirukumab, sarilumab, mavrilimumab, abatacept, belimumab
 - IL-12/23 inhibitors (ustekinumab)
 - IL-17 inhibitors (secukinumab, ixekizumab, brodalumab)
 - tyrosine kinase inhibitor (nintedanib)
 - Any live viral or live bacterial vaccination
 - Rituximab
 - Any cytotoxic agents (cyclophosphamide, chlorambucil, nitrogen mustard, or other alkylating agents)
 - Intravenous immunoglobulin (IVIG), apheresis therapy (plasmapheresis or leukapheresis)
 - Systemic immunosuppressive agents (including but not limited to cyclosporine A, azathioprine, tacrolimus, sirolimus, methotrexate, sulfasalazine, leflunomide with cholestyramine washout or mycophenolate mofetil/mycophenolic acid)
 - Intramuscular, intra-articular, intrabursal, epidural, intralesional or IV GCs
 - Pirfenidone
 - Systemic and topical Janus kinase inhibitors (eg, tofacitinib, upadacitinib)
 - Other biologics
 - Any investigational agents/treatments
- Treat with rescue therapy before Week 24, including:
 - 1) Oral Corticosteroid \leq 20 mg/day of prednisolone or equivalent
 - 2) Immunomodulator (Azathioprine), within the approved dose for SSc
- New start of oral Corticosteroid (prednisolone or equivalent) before Week 24.
- Significant increase of oral Corticosteroid (prednisolone or equivalent) before Week 24.

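### Azathioprine is both prohibited throughout the study and allowed as rescue after Week 24, with no written exemption, so the stopping rule and one supplementary Week 52 analysis conflict with the rescue provision

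*Protocol*

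**What the plan says.** **Protocol 6.8, prohibited list.** Under a heading that applies throughout the study, the systemic immunosuppressants listed include "cyclosporine A, azathioprine, tacrolimus, sirolimus, methotrexate, sulfasalazine, leflunomide with cholestyramine washout". The list ends with: "The sponsor must be notified in advance (or as soon as possible thereafter) of any instances in which prohibited therapies are administered".

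**Protocol 6.8, rescue.** If mRSS has risen by at least 5 from baseline, the investigator may give rescue after Week 24. The options are oral corticosteroid up to 20 mg/day of prednisolone or equivalent, or "Immunomodulator (Azathioprine), within the approved dose for SSc". The paragraph ends: "If rescue therapy as stipulated above fails to control SSc symptoms sufficiently, the investigator should consider discontinuing the patient from the study".

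**Protocol 6.8, oral corticosteroids.** "Increases in corticosteroid doses for treatment of SSc are not allowed during the study". No exception is made for rescue.

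**Protocol 7.1.** Study intervention must be discontinued if "The participant initiates treatment with prohibited therapies listed in Section 6.8 unless agreed upon with the sponsor medical monitor". After such a stop, "the assessments should be obtained as specified in the SoA".

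**SAP Appendix 11.** The first bullet defines a prohibited change in SSc medication as "New start of prohibited and restricted therapies during the study which are defined in the protocol Section 6.8". It reproduces the list, azathioprine included, with no time limit. Separate bullets cover rescue therapy and new or increased oral corticosteroid, each only before Week 24.

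**SAP 5.4.2.2 and 5.4.2.4.** For Week 52 endpoints there are three intercurrent events: (1) a prohibited change, (2) discontinuation for lack of efficacy or an AE of SSc, and (3) start of rescue after Week 24. All three take the composite strategy, which is zero change for continuous endpoints. The supplementary analysis in 5.4.2.4 moves only event 3 to treatment policy.

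**The concern.** A site that gives azathioprine as permitted rescue has two instructions. The rescue paragraph leaves the choice to the investigator and raises discontinuation only if rescue fails. Section 7.1 requires study drug to stop unless the medical monitor agrees, and the rescue paragraph does not mention that agreement.

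The same overlap reaches the SAP. One act, starting azathioprine after Week 24, meets event 1 and event 3, and nothing says which takes precedence. The only change that 5.4.2.4 makes is to use data after rescue. As written, it would do so for participants rescued with steroid but not for those rescued with azathioprine. The result would depend on which allowed drug was chosen and on how the programmer resolves the overlap.

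**Working it through.** **1. Where the overlap matters.** Azathioprine rescue after Week 24, under each reading:

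| Use | Counted as prohibited change (event 1) | Counted as rescue only (event 3) | Differs? |
|---|---|---|---|
| Study drug, Protocol 7.1 | Stop unless medical monitor agrees | Continue | Yes |
| Week 24 primary analysis | Not applicable; rescue starts after Week 24 | Not applicable | No |
| Main Week 52 mRSS analysis, SAP 5.4.2.2 | Zero change | Zero change | No |
| Time to disease worsening, SAP 5.5.2 | Event | Event | No |
| Supplementary Week 52 mRSS, SAP 5.4.2.4 | Zero change | Observed value | Yes |

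SAP 5.5.2 has a first-occurrence rule, but it applies only to time to disease worsening. Oral steroid rescue after Week 24 does not create the SAP overlap, because oral steroids are not on the prohibited list and the steroid bullets in Appendix 11 end at Week 24.

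**2. Doses and visits at stake per participant** (Protocol Table 1).
- Main-study doses at Weeks 0, 4, …, 48: 48/4 + 1 = 13. After Week 24 (28, 32, 36, 40, 44, 48): 6.
- Post-baseline mRSS visits at Weeks 4, 8, …, 52: 52/4 = 13. After Week 24 (28 to 52): 7.

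**3. Shift in the arm mean at Week 52.** The planned arm size is 28 (Protocol 9.2). If one participant with true change d is scored zero, the raw arm mean moves by d/28 (observed minus zero-scored). The documents give no value for d, so a range of −10 to +10 is assumed:

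| d | −10 | −5 | 0 | +5 | +10 |
|---|---|---|---|---|---|
| Shift | −0.36 | −0.18 | 0 | +0.18 | +0.36 |

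A lower mRSS is better. Zero-scoring a participant who remains 5 points worse makes that arm look 0.18 better; zero-scoring one who has fallen 5 points below baseline makes it look 0.18 worse. With k such participants in one arm the shift is k·d/28. For example, three with d = +5 give 15/28 = 0.54.

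**4. Covariate adjustment.** This is a single-visit approximation to the MMRM. It assumes complete data, 28 per arm, baseline mRSS uniform on 10 to 22, and 50% prevalence each for ILD and anti-topoisomerase I. Over 5000 simulated designs, the shift in the adjusted treatment difference for d = 5 averages 0.18 (95% range 0.10 to 0.27). The two prevalences are assumptions and are not in the documents.

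**5. Scale.** Taking the planning SD of 8 to hold at Week 52, the standard error of the difference is 8 × √(2/28) = 2.14. A shift of 0.18 is about 8% of that.

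**The case against.** The best case against is that the intent is clear.

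- The list covers restricted as well as prohibited therapies, and a drug barred in general but allowed in one situation fits the former. Section 7.1 names only prohibited therapies.
- Protocol 4.1.1 speaks of rescue medication in the LTE separately from prohibited medication and leaves it to the investigator.
- The agents that the benefit-risk table links to discontinuation do not include azathioprine.
- Appendix 11 has its own bullet for rescue before Week 24, which suggests later rescue was not meant to count as a prohibited change. Section 5.4.2.2 treats later rescue as a separate event.
- Medical-monitor agreement can avoid the stop.
- The effect is confined to one supplementary analysis with nominal p-values.

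These points make an exemption the likely intent, but none of them writes one. The restricted label does not help the SAP, since Appendix 11 covers both classes, and Protocol 6.8 itself calls the listed drugs prohibited when it requires notification. The benefit-risk list is not exhaustive; it also omits rituximab as an on-study trigger. The rescue bullet before Week 24 overlaps the first bullet for azathioprine on any reading, so redundancy proves little. Medical-monitor agreement is a release that the rescue paragraph never tells the site to seek.

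The point about small numerical effect stands. So does the point that d = −10 is an extreme case: it needs a fall of at least 15 points after the qualifying rise of 5.

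**Conclusion.** The concern holds. Followed literally, Protocol 7.1 stops study drug for a permitted rescue unless an unmentioned agreement is obtained, and SAP 5.4.2.4 handles two permitted rescue drugs differently. The reach is narrow: trial conduct after azathioprine rescue and one supplementary analysis. The overlap leaves the primary result, the main Week 52 analysis and time to disease worsening unchanged, and participants who stop study drug still have assessments scheduled.

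The documents give neither a rescue rate nor a steroid/azathioprine split, so the total effect cannot be stated and may be nil. The per-participant shift of 0 to 0.36 points rests on 28 per arm and on the assumed range for the Week 52 change. This should be corrected because a mandatory stopping rule and an intercurrent-event definition ought not to depend on how a site or programmer guesses the intent.

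**What to change.** 1. In the Protocol 6.8 prohibited list, after azathioprine, add: *except azathioprine given as protocol-allowed rescue after Week 24*. Section 7.1 then follows by reference.
2. Add the same phrase to the first bullet of SAP Appendix 11. Azathioprine rescue after Week 24 is then event 3 only, and 5.4.2.4 treats both rescue drugs alike.
3. In the Protocol 6.8 sentence barring corticosteroid increases for SSc, add: *except as rescue after Week 24*.

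The SAP edit alone is not enough. If a site stops study drug under 7.1 and records lack of efficacy, event 2 applies and stays composite in 5.4.2.4.

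The cost is a few words. The protocol part needs an amendment with the usual ethics committee approval and investigator signature, so it could go with the next planned amendment. No new procedures or data are needed.
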